
B3. MILITARY RELEVANCE

Military personnel often engage in sustained physical activity while time to eat and availability of food is limited (4, 36, 37). Under such conditions, it is likely that skeletal muscle glycogen stores are depleted, reducing the service member's ability to maintain an optimal level of physical performance. However, during 'real-world' military training operations there is limited knowledge regarding altered carbohydrate metabolism at the skeletal muscle level, as invasive investigations requiring muscle biopsies cannot be conducted during training operations. Identifying the mechanism, as well as determination of non-invasive markers of molecular pathways regulating carbohydrate metabolism is critical to move findings from controlled laboratory settings to field operations. Modeling of circulating microRNA may allow for a more comprehensive understanding of nutrient adequacy during military operations, allowing for implementation of targeted nutrition interventions to optimize military performance. Support for this protocol comes from Defense Health Program (DHP) Research funds, under Joint Program Committee-5 Nutrition and dietary supplements working group.

B4. OBJECTIVES/SPECIFIC AIMS/RESEARCH QUESTIONS

Objectives

1. Determine the influence of carbohydrate availability (e.g., glycogen depletion and repletion) on skeletal muscle microRNA expression, and if changes in circulating microRNA are reflective of changes in skeletal muscle microRNA.

1 2. Determine how initiation of exercise with adequate or low glycogen stores effects exogenous
2 carbohydrate efficiency.

3

4 **Hypotheses**

5

6 1. Expression of microRNA in skeletal muscle will be influenced by alterations in glycogen status, and
7 that these changes in skeletal muscle microRNA will be associated with modulation in circulating
8 microRNA.

9

10 2. Exogenous carbohydrate efficiency will be greater when exercise is initiated with lower glycogen
11 stores. Increased efficiency will be associated with higher phosphorylation of IRS-1 and AMPK.

12 **B5. RESEARCH PLAN**

13

14 **B5.1 Research Design**

15 This study will be a randomized cross-over placebo control trial.

16

17 **B5.2 Research Subjects/Population(s)**

18

19 **B5.2.1 Subject Population(s)**

20 Subject population will be representative of active duty male and female service members, being in good
21 health and recreationally active.

22

23 **B5.2.2 Number of Subjects, Records, and/or Specimens**

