Following identification of skeletal muscle microRNA that had a significant change, Taqman® probes (Applied Biosystems) will be used to assess the expression of these microRNA in serum to determine their potential use as noninvasive markers of altered carbohydrate metabolism following glycogen depletion and repletion. Total circulating miRNA will be extracted from 200 μ L serum using miRNeasy Serum/Plasma kit, which allows for extraction and purification of small (< 200 nt) cell-free RNA (Qiagen, Valencia, CA, USA). Exosomal circulating miRNA will also be extract from 1000 μ L serum using miRCURY™ RNA Isolation Kit to measure miRNA. To avoid introduction of potentially contaminating material, prior to RNA extraction serum samples will be centrifuged for 10 min at 4°C to remove cellular debris. Supernatant will be removed and transferred to a new tube without disturbing the pellet. Due to the small amount of RNA in the serum, 3.5 μ L of a Spike-In Control (C. elegans miR-39; Qiagen) will be added to all samples prior to extraction of RNA to determine the yield of template recovered. After extraction 3 μ L of serum RNA will be reverse transcribed using the TaqMan® microRNA RT kit (Applied Biosystems) with miRNA-specific stem-loop RT primers pooled in 1X-Tris-EDTA (TE) buffer for a final dilution of 0.05X. A pre-amplification step will be performed after reverse transcription to increase cDNA template using a primer pool of 20 X Taqman® Small RNA Assays (Applied Biosystems) for miRNA of interest at 0.05X concentration in 1X TE buffer. All serum miRNA will be normalized to the geometric of external (Spike-In Control C. elegans miR-39) and internal controls to allow for both technical and inter-individual normalization (47). Geometric mean of controls will be used to correct for possible outlying values and abundance differences between the different controls (48).

All reverse transcription for mRNA and miRNA, and pre-amplification of serum miRNA will be conducted in a T100™ Thermal Cycler (Bio-Rad, Hercules, CA). A StepOnePlus™ real-time PCR system (Applied Biosystems) will be used to perform all mRNA and miRNA analysis. Fold changes will be calculated using the $\Delta\Delta C_T$ method as described below in statistical analysis section.

Bioinformatics Analysis

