32 Hard copy data records will be stored for a minimum of three years from the time the study is completed.
33 Electronic data records will be maintained for a period of at least five years after the study has been
34 completed.
35

36 **B5.6 Managing Data and/or Human Biological Specimens for Future Research**

37 Any use of the samples outside of this defined protocol will be submitted as a protocol amendment or a
38 new protocol. Samples will be retained for future analyses once the protocol is closed if the subject
39 provided permission in the informed consent document.
40

41 **B5.8 Statistical Analysis**

42 **B5.8.1 Sample Size Estimation**

43 Statistical power and sample size were determined using the minimum fold change required for a
44 physiologically relevant difference in microRNA expression. Variance (standard deviation) was based
45 on recent publications assessing change in microRNA expression in skeletal muscle (18, 50, 51) and
46 circulating (34, 35, 52) in response to an acute bout of exercise. Using this information the sample
47 size necessary to determine statistical significance between intervention arms, with a mean fold
48

1 change of 1.5 ± 1 is 9 per group, with an alpha of 0.05 and 80% power. In the present study, 12
2 volunteers will be studied in a repeated measures crossover design to account for potential greater
3 inter-individual variability.
4

5 **B5.8.2 Data analysis**

7 Statistical analyses will be conducted using either SPSS (IBM Corp. Armonk, NY), SAS 9.3 (SAS
8 Institute Inc., Carey, NC), or equivalent. Common descriptive statistics will be used to describe
9 volunteer characteristics. Shapiro-Wilk tests will be used to determine normality of data. Mixed
10 model repeated measures ANOVA will be performed to determine main effects of time (baseline,
11 immediately, 3-hr, and 24-hr post glycogen depletion), carbohydrate intake ($6.0 \text{ g} \cdot \text{kg}^{-1} \cdot \text{d}^{-1}$ versus $1.5 \text{ g} \cdot \text{kg}^{-1} \cdot \text{d}^{-1}$) and time-by-carbohydrate interactions for skeletal muscle and circulating microRNA, mRNA
12 expression, and markers of nutritional status. If interactions are significant, Bonferroni correction will
13 be used to examine these relationships. Correlation coefficients and multiple regression analysis will
14 be used to evaluate relationships between study outcome measures. The alpha level will be adjusted

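### The muscle-serum association in Objective 1 has no specified model; if times are pooled without a time term, the response to the ride alone can produce a correlation

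*Combined protocol and SAP*

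**What the plan says.** Objective 1 in B4 has two parts. The first concerns the "influence of carbohydrate availability (e.g., glycogen depletion and repletion) on skeletal muscle microRNA expression". The second asks "if changes in circulating microRNA are reflective of changes in skeletal muscle microRNA". Hypothesis 1 repeats the second part as an expectation that "these changes in skeletal muscle microRNA will be associated with modulation in circulating" microRNA.

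B5.8.2 specifies a mixed "model repeated measures ANOVA will be performed to determine main effects of time (baseline", "immediately, 3-hr, and 24-hr post glycogen depletion), carbohydrate intake" and their interaction. It is run on muscle and on circulating microRNA, each as an outcome. The association between the two tissues falls under a separate sentence, which opens "Correlation coefficients and multiple regression analysis will" and runs on: "be used to evaluate relationships between study outcome measures. The alpha level will be adjusted" for multiple comparisons. That sentence does not single out the muscle-serum pair, say whether times and arms are pooled, or name any model term.

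The serum panel is chosen from muscle results. In B5.4 (mRNA and microRNA Expression) the serum assays come "Following identification of skeletal muscle microRNA that had a significant change". The section does not say whether that change is over time, between arms, or an interaction. It then gives the purpose of the serum assays: to see whether these microRNA could serve as markers of carbohydrate metabolism without a biopsy.

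**The concern.** The ANOVA can show that muscle microRNA change and that serum microRNA change. It cannot show that one tracks the other. That half of the primary objective rests on the correlation and regression sentence alone.

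Three features of the design make the missing specification matter:

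- Both arms ride to failure before the second biopsy, so any microRNA that responds to the ride shifts in both arms.
- The beverage starts only after the second biopsy (B5.3, Carbohydrate Supplementation). The baseline and immediate samples, 12 × 2 × 2 = 48 of the 96 pairs, therefore carry no carbohydrate contrast.
- Serum assays are run on microRNA already found to change in muscle. If that change is over time, a muscle time course is built in by selection, and any serum shift after the ride, from whatever tissue, will line up with it.

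A serum microRNA that only responds to exhausting cycling could then appear to reflect muscle, and be carried forward as a marker of carbohydrate state.

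**Working it through.** **The plan's own figure.** B5.8.1 gives 9 per group for 1.5 ± 1 at alpha 0.05 and 80% power. A two-sided two-sample t-test with difference 1.5 and SD 1 gives n = 8.06, rounded up to 9, so the figure reproduces. It concerns a difference between arms and gives no size for the association.

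**Inputs from the documents.** 12 volunteers, 2 arms and 4 times (B5.8.1, B5.8.2): 12 × 2 × 4 = 96 muscle-serum pairs, 8 per person.

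**Assumptions, because the documents give no values.** Total SD is 1 in each tissue. The correlation between repeated measurements of one tissue in one person is 0.5, so the within-person variance is 0.5. Both tissues share a mean profile of 0, k, k, k/2 at baseline, immediately, 3-hr and 24-hr. Otherwise muscle and serum are independent, and carbohydrate has no effect.

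**Expected correlation with a participant term and no time term.** The variance of the profile over the four times is k² × [(0 + 1 + 1 + 0.25)/4 − (2.5/4)²] = k² × (0.5625 − 0.3906) = 0.1719k². Per person, the shared shift contributes 8 × 0.1719k² = 1.375k² to the sum of squares, and noise contributes 7 × 0.5 = 3.5. Hence

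r ≈ 1.375k² / (1.375k² + 3.5).

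The degrees of freedom are 96 − 12 − 1 = 83. The two-sided 5% critical value is 1.989/√(1.989² + 83) = 0.213.

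**Fisher-z check.** The standard error is 1/√82 = 0.110, and atanh(0.213) = 0.217. At k = 1, r = 0.282, atanh(r) = 0.290 and (0.290 − 0.217)/0.110 = 0.66, a rejection rate of about 75%. At k = 0.75, r = 0.181 and the rate is about 38%. At k = 0.5, r = 0.089 and it is about 13%. Simulation agrees:

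| Shared shift k (total SD) | Expected r | Participant only, alpha 0.05 | Participant only, alpha 0.005 | Participant + time, alpha 0.05 |
|---|---|---|---|---|
| 0.5 | 0.09 | about 12% | about 2% | about 5% |
| 0.75 | 0.18 | about 38% | about 11% | about 5% |
| 1.0 | 0.28 | about 76% | about 43% | about 5% |

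The 0.005 column assumes ten tests sharing 0.05; with time added, the rate there is about 0.5%. At k = 0.25, r is 0.024 and the excess over 5% is negligible.

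**Sensitivity at alpha 0.05, participant term only.**

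- At k = 1.0 the rate is about 52% for within-person correlation 0.3 and 98% for 0.7.
- A shift of 1.0 SD in muscle but 0.5 SD in serum gives about 31%.
- The profile 0, k, k/2, 0 has the same variance, 0.1719k². A separate simulation with it, at a shift of 1 within-person SD (1/√2 = 0.71 total SD), gave 31.8%.
- In that second set-up, at a shift of 1.5 within-person SD, the participant term raised the rate from 43.0% (all 96 pairs pooled, no adjustment) to 83.6%. Removing between-person noise leaves the shared time course more dominant.
- Also in that set-up, change scores pooled over the post-ride times with a participant term gave 19.3% to 76.4% at shifts of 1 to 2 within-person SD.

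**Analyses not affected.** Change from baseline at one time in one arm (n = 12) gave 4.4% to 5.6%. Between-arm differences at 3-hr (n = 12) gave 5.1% to 5.6%.

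**Power of the arm-difference correlation.** With 12 pairs, 80% power at 0.05 needs |r| = tanh[(1.960 + 0.842)/√9] = 0.73.

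**The case against.** The plan is silent; it does not prescribe a model without time. A reader might infer from B5.8.2 that time will be left out, but multiple regression can include it and correlations may be computed one time at a time. This stands: the consequence is conditional on pooling.

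A reader might also infer that the randomised contrast plays no part in judging serum microRNA. The documents do not support that. The ANOVA is specified for circulating microRNA with a time-by-carbohydrate term, so a serum microRNA that responds only to cycling should show a time effect and no interaction beyond chance. This stands, but the ANOVA does not test whether serum tracks muscle, and the plan does not require both results before a marker is proposed.

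Objective 1 counts depletion as well as repletion as carbohydrate availability, and the ride produces the depletion. Co-movement after the ride is therefore partly within the question, and calling it a false positive presumes that individual tracking is the target. This stands in part. Within an arm, depletion cannot be separated from the exercise that caused it, so co-movement alone does not establish a marker of carbohydrate status.

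On size, reading the plan's 1.5 ± 1 as the shared shift would push the rate above 99%. That figure describes a difference between arms, and the documents give no shift common to both. The planned alpha adjustment also lowers the rates, as the 0.005 column shows.

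**Conclusion.** The concern holds in conditional form. B5.8.2 leaves the muscle-serum association unspecified. Pooling the four times and two arms under the named methods, with or without a participant term, lets the mean response to the ride pass for serum tracking muscle. For shared shifts of 0.5 to 1.0 total SD and a within-person correlation of 0.5, the participant-adjusted false-positive rate is about 12% to 76% at 0.05, or about 2% to 43% at 0.005. A time factor brings it back to nominal. The shift, the correlation and the ten-test adjustment are assumptions; with a shift of 0.25 SD or less there is no practical problem. The documents do not show that a time-free analysis is intended, or that the carbohydrate evidence on serum microRNA is absent. The change is still worth making, because it concerns half of the primary objective and the choice is otherwise open after the data are seen.

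**What to change.** In B5.8.2:

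1. State that the muscle-serum association is estimated with participant, period and time (a four-level factor) in the model.
2. Report the across-time correlation separately, as a description of the shared exercise and depletion response.
3. Before a serum microRNA is called a marker of carbohydrate status, also report, as supportive evidence, the correlation between the within-person CHO-minus-CON difference in serum and the same difference in muscle, at 3-hr and at 24-hr.

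This takes a few sentences and no new data. The adjusted association will be smaller and less precise than a pooled correlation. The arm-difference correlation rests on only 12 pairs per time, enough to detect only a very strong relation, so a null result there should not be read as absence of association.

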12 subtracting exogenous glucose oxidation from total CHO oxidation. The first 40 min of steady-state
13 exercise will allow for equilibration between the $^{13}C/^{12}C$ in expired CO_2 and the $^{13}C/^{12}C$ in CO_2 produced in
14 tissues (45). Thus, endogenous glucose oxidation will only be calculated from samples obtained in the last
15 40 min of steady-state exercise (40 to 80 min).

16

17 *Muscle Glycogen*

18 Approximately 20 mg of muscle will be dehydrated in a freeze dryer. Samples will then be ground to
19 powder and visible connective tissue will be removed. Powdered muscle will be placed in 500 μ l 2 N HCl.
20 Samples will then be placed in an incubator for 120 min at 100 °C. Following incubation samples will be
21 neutralized with 1500 μ l 0.67 N NaOH. Muscle glycogen will be in solution at this point. Glycogen will be
22 quantified by a fluorometric assay (Sigma-Aldrich, St. Louis, MO, USA).

23

24 *Intramuscular Triglyceride Concentrations*

25 Intramuscular triglyceride concentrations will be determined using the Folch method (46). Dehydrate
26 muscle will be homogenized in a 2:1 chloroform-to-methanol solvent. Following extraction, samples will be
27 saponified in ethanolic KOH at 60 °C, and glycerol content will be determined using a commercially available
28 colorimetric assay (Sigma)

29

30 *mRNA and microRNA Expression*

31 Total RNA will be isolated from approximately 25 mg of muscle using a mirVana™ miRNA isolation kit
32 (Invitrogen, Carlsbad, CA, USA). Quantity and quality of RNA will be assessed using a Nanodrop ND-
33 1000spectrophotometer (Nanodrop, Wilmington, DE, USA). Equal amounts of total RNA will be
34 synthesized into cDNA for analysis of mRNA (iScript™ Advanced cDNA Synthesis Kit; Bio-Rad) and a
35 TaqMan® microRNA RT kit (Applied Biosystems, Foster City, CA, USA). Individual primers will be used to
36 determine the mRNA expression of known intracellular targets regulating muscle metabolism, to include
37 but not limited to PGC-1 α , SIRT1, ACC, AMPK, PDK4, IRS1, and GLUT4. miRNA (20-40 bp) will be size-
38 selected from total RNA using Illumina's protocol (US Army Center for Environmental Health Research,
39 Frederick, MD). The sorted miRNA will be tagged and assayed using the Illumina NextSeq instrument.
40 Briefly, 500 ng total RNA will be used to construct sequencing libraries. Subsequently, the samples will be

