41 amplified using index-tagged primers to facilitate multiplexing. The amplified cDNA constructs will be size-
42 selected, quality controlled before loading to the NextSeq instrument to generate 50 base reads. Image
43 analysis and base calling will be performed using the Illumina pipeline.

44

45 Preprocessing of raw base calls, sample de-multiplexing, trimming and filtering will be similar to that
46 described in 'Analysis of sequencing output'. For the miRNA quantification/enrichment, reads are first
47 aligned to the Rfam RNA database to filter and profile other small RNA species in the samples. Then reads
48 are mapped for small RNA annotation against reference zebrafish mature mature RNA sequences from the
49 miRBASE database. The miRNA read count matrix for each sample will be generated using open source
50 tools such as PICARD.

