15 for multiple comparisons, with the level for statistical significance set at $P < 0.05$.
16

20 **SECTION C: HUMAN RESEARCH PROTECTIONS**

21 **C1. RECRUITMENT AND CONSENT**

24 **C1.1 Identification and Selection of Subjects**

26 Potential volunteers will be recruited from the U.S. Army Natick Soldier Center pool of military volunteers
27 during a face-to-face briefing as described in the below *Recruitment Process* section. Additional volunteers
28 will be recruited from civilian population and active duty military stationed at the U.S. Army Natick Soldier
29 Center, as well as civilians from the local surrounding area using flyers and electronic posting (**Appendix**
30 **G**)

32 **C1.2 Recruitment Process**

34 Superiors of Service members (e.g., unit officers, senior NCOs, and equivalent civilians) / supervisors of
35 DoD civilians (e.g., military and civilian supervisors or anyone in the supervisory structure) shall not be
36 present at any recruitment sessions or during the consent process in which members of units under their
37 command / personnel under their supervision are afforded the opportunity to participate as human subjects
38 of research.

40 For Soldiers in the U.S. Army Natick Soldier Center pool of military volunteers, the Principal Investigator
41 will furnish a copy of the consent form to the Human Research Subjects Program Coordinator or designee.
42 The Coordinator will schedule the consent briefing for the military human research volunteer platoon and
43 will serve as ombudsman during the briefing. Civilians and permanent party military will be recruited for the
44 study using posted or electronically distributed or though informational briefs. Principal Investigator or
45 Project Coordinator will receive and respond to inquiries submitted from these recruitment materials, and
46 will schedule informed consent briefings for these potential volunteers. Potential volunteers not in the U.S.
47 Army Natick Soldier Center pool of military volunteers will be briefed one-on-one by the Principal
48 Investigator or Project Coordinator.

49 **C1.3 Eligibility**

1 All potential volunteers will complete the background questionnaire (**Appendix H**). Volunteers must be
2 medically cleared by the Office of Medical Support and Oversight (OMSO) for participation in accordance
3 with USARIEM procedures outlined for screening volunteers for research involving exercise. Potential

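### Does the plan need to name a multiplicity method, and the model term that defines a significant change, for the sequenced muscle microRNAs?

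*Combined protocol and SAP*

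**What the plan says.** Objective 1 in B4 is to "Determine the influence of carbohydrate availability (e.g., glycogen depletion and repletion) on skeletal muscle microRNA expression" and to see whether circulating microRNA follow the muscle changes.

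The mRNA and microRNA Expression part of B5.4 describes sequencing of the muscle small-RNA fraction: "The sorted miRNA will be tagged and assayed using the Illumina NextSeq instrument", and "The miRNA read count matrix for each sample will be generated using open source" tools. Muscle microRNAs found to change significantly are then measured in serum by PCR. Under Bioinformatics Analysis they also go into a pathway tool, whose output guides further gene and protein targets. Some targets are named in advance; primers will "determine the mRNA expression of known intracellular targets regulating muscle metabolism, to include" a listed set.

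B5.8.2 fits a repeated measures model with three terms: time (four levels), carbohydrate intake (two levels) and their interaction. Outcomes are muscle and circulating microRNA, mRNA "expression, and markers of nutritional status. If interactions are significant, Bonferroni correction will" be used to follow up. The section ends: "The alpha level will be adjusted" "for multiple comparisons, with the level for statistical significance set at" P < 0.05.

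The sample size in B5.8.1 concerns a single comparison: a mean fold "change of 1.5 ± 1 is 9 per group, with an alpha of 0.05 and 80% power". Twelve volunteers are to be studied in the crossover.

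**The concern.** The one named correction, Bonferroni, follows up an interaction within an outcome. It does not govern how many microRNAs reach the selected list. The sentence on alpha could cover the whole screen, but it gives neither a method nor a family. The screen also tests three terms per microRNA, and B5.4 does not say which of them makes a change significant.

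The muscle half of Hypothesis 1, the choice of serum assays and the pathway input all rest on that list. Too loose a rule would fill it with false hits. Too strict a rule, with 12 people and a sample size set for one comparison at 0.05, could leave it short. A method chosen after the data are seen would let the analyst choose between the two. Objective 2, on exogenous carbohydrate use, does not depend on the list.

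**Working it through.** **The plan's own figure.** Inputs from B5.8.1: difference 1.5, SD 1, alpha 0.05, power 80%; two-sided testing is assumed. A two-sample t-test gives power 79.7% with 8 per group and 84.8% with 9, so 9 per group is reproduced. The calculation covers one comparison and leaves nothing for correction across microRNAs.

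**False selections with no correction across microRNAs.** The number tested, m, is not in the documents; 100 to 500 is assumed here.
- One term at 0.05: expected false selections are m × 0.05, which is 5 for m = 100 and 25 for m = 500 if nothing changes.
- Any of three terms at 0.05: the rate per microRNA is 1 − 0.95³ = 0.143, which gives about 14 and 71. A null simulation of the 2 × 4 within-person model with 12 people (20,000 runs) also gives 0.143.

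**Power under strict correction.** The test is the interaction F on 3 and 33 degrees of freedom, with 12 people and an arm difference of 1.5 at one of four times. With SD the standard deviation of the arm difference, and ρ the correlation of those differences between time points within a person, the noncentrality is

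12 × 1.5² × 0.75 / [SD² × (1 − ρ)].

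An SD of 1 reads the stated SD as that of the difference. An SD of 1.41 = √2 reads it as the within-arm SD with no correlation between arms.

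| SD | ρ | Noncentrality | Power at 0.05 | Bonferroni, m = 100 | Bonferroni, m = 500 |
|---|---|---|---|---|---|
| 1 | 0 | 20.25 | 95.9% | 48.5% | 29.9% |
| 1.41 | 0 | 10.125 | 71.1% | 12.9% | 5.5% |
| 1 | 0.5 | 40.5 | >99% | 94% | 84% |
| 1.41 | 0.5 | 20.25 | 95.9% | 48.5% | 29.9% |

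A heavy loss of power from Bonferroni therefore holds for some inputs and not for others, and the documents fix neither SD nor ρ. The reading of 1.5 matters as well. If it is a ratio against a null of 1, the difference is 0.5. At ρ = 0 the noncentrality is then 12 × 0.5² × 0.75 / SD² = 2.25 or 1.125, and power at 0.05 is 19% or 12% before any correction.

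**A false discovery rate in between.** In simulation (4,000 runs, m = 100 to 500, 5–20% of microRNAs changing, ρ = 0, independent microRNAs), Benjamini-Hochberg at 5% keeps 4–5% of the list false. Power is 64–83% at SD 1 and 12–30% at SD 1.41. With m = 100, 5 changing and SD 1.41, the list is empty in 44% of runs. At 10%, power is 76–91% and 20–45%, with 8–10% of the list false.

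**Which term.** Depletion by exercise happens in both arms, so it appears as a time effect. The effect of repletion appears as the time-by-carbohydrate interaction. Objective 1 names both, and B5.4 wants serum markers for both. No single term covers the objective.

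**Which microRNAs.** B5.4 says the PCR system performs all mRNA and microRNA analysis, which seems to conflict with sequencing. That sentence closes the PCR paragraphs, and B5.5 confirms that muscle RNA is shipped for microRNA sequencing. The muscle screen is the sequenced set.

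**The case for a change.** The strongest argument for a change is that a promise to adjust, with no method or family, lets the choice be made after the data are seen, between rules that differ greatly in false share or power. Hypothesis 1 is stated as a hypothesis, so calling the work exploratory does not remove the point. The remedy would be a few sentences, with no new samples or assays.

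Part of this stands: the method, the family and the selecting term are unstated, and writing them down before unblinded analysis would be good practice. What does not stand is the step from silence to harm. The damaging case applies no correction at all across microRNAs, which the closing sentence of B5.8.2 does not invite. Milder readings are also available. Requiring a Bonferroni-significant time-point difference after a significant interaction, for example, selects about 2.0% of unchanged microRNAs in simulation, or 2 to 10 for m = 100 to 500, against 5 to 25 at raw 0.05.

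The obvious remedy also has costs. Making the interaction the only gate would keep depletion-responsive microRNAs common to both arms out of the serum panel. A 5% false discovery rate has low power at the larger SD, and 10% is as defensible. Those choices call for judgement about the assay and its variability, on which the documents say too little to settle them here.

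**Conclusion.** No change to the plan is called for. The gap is missing detail that an analyst can fill sensibly: adjust across the sequenced microRNAs, as B5.8.2 already commits to do, and report which term each selected microRNA passed on. A false discovery rate or a Bonferroni rule across microRNAs would each be faithful to the text and control error over the screen.

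The one firm figure is the null selection rate with no correction across microRNAs: 5% per microRNA for one term and 14.3% if any of three counts, taking the three tests as independent. Counts of false hits need an assumed number of microRNAs. Power figures need that number, the SD of the arm difference, the correlation across time points and a reading of 1.5 ± 1; Bonferroni power with 100 microRNAs runs from 13% to 94% over the cases in the table. The material therefore does not establish that strict correction would miss most real changes, or that one rule is clearly better than another.
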